3.5 Handling of Endpoints

3.5.1 Cohen-Mansfield Agitation Inventory (CMAI)

The CMAI total score will be the sum of scores for 29 CMAI items.

The CMAI Aggressive Behavior score will be the sum of scores for CMAI Items 3, 4, 7, 8, 9, 10, 11, 13, 14, 15, 21, and 25.

The CMAI Physically Non-aggressive Behavior score will be the sum of scores for CMAI Items 1, 2, 16, 22, 26, and 29.

[figure not shown]
The CMAI Verbally Agitated Behavior score will be the sum of scores for CMAI Items 5, 6, 18, and 19.

3.5.2 Clinical Global Impression - Severity of Illness (CGI-S)

"0. Not assessed" will be handled as missing data.

3.5.3 Clinical Global Impression - Improvement (CGI-I)

"0. Not assessed" will be handled as missing data.

3.5.6 Drug Induced Extra-Pyramidal Symptoms Scale (DIEPSS)

The DIEPSS total score will be the sum of scores for DIEPSS items 1 through 8.

3.5.7 Abnormal Involuntary Movement Scale (AIMS)

The AIMS total score will be the sum of scores for AIMS items 1 through 7.

3.5.8 Sheehan Suicidality Tracking Scale (S-STS)

The S-STS total score will be the sum of scores for Item 1a, Items 2 through 11, highest of Item 12 or any row of Item 16, highest of Item 14 or any row of Item 15, Item 17, and Item 20.

The S-STS suicidal ideation subscale score will be the sum of scores for Items 2 through 11.

The S-STS suicidal behavior subscale score will be the sum of scores for Item 1a, highest of Item 12 or any row of Item 16, highest of Item 14 or any row of Item 15, Item 17, and Item 20.

3.5.9 Alzheimer's Disease Cooperative Study - Activities of Daily Living (ADCS-ADL)

The ADCS-ADL total score will be the sum of scores for ADCS-ADL Items 1 through 19.

3.5.10 Mini-Mental State Examination (MMSE)

The MMSE total score will be the sum of scores for MMSE Items 1 through 30.

4 Sample Size

In Trial 331-12-283, which was performed outside Japan, the 2 mg fixed-dose group showed superiority over the placebo group in patients with aggression (patients with aggressive behavior at baseline), thus suggesting that it may also be the optimum dose for Japanese patients. Efficacy was not observed in the 1 mg fixed-dose group, but in Trial 331-12-284, the efficacy of a dose less than 2 mg was suggested by the results obtained in patients from the flexible-dose (0.5 to 2 mg) group, who had aggression.

In this trial, a power of detection $\geq 80\%$ will be achieved for comparison between the placebo group and the 1 mg group to allow evaluation of superiority over the placebo group if equivalent efficacy is demonstrated in the 1 and 2 mg groups. For comparison between the 2 mg group (possible optimum dose) and the placebo group, a more sufficient power of detection will be obtained by changing the randomization ratio. In this trial, it is assumed that the difference between the 2 mg group and the placebo group in the change in the CMAI total score from baseline to Week 10 is -5.35, and the standard deviation (calculated from the standard error of the difference between the 2 mg and placebo groups and the number of subjects at baseline) is 15.06 on the basis of the results of Trial 331-12-283. By setting the number of subjects in the 2 mg group, 1 mg group, and placebo group as 148, 111, and 148, respectively (randomization ratio of 4:3:4), the power of detection is 86.1% for the comparison between the 2 mg group and the placebo group and is 80.5% for the comparison between the 1 mg group and the placebo group in a test with a significance level of 5% (two sided).

On the basis of the above considerations, the number of subjects will be set at 148 in the 2 mg group, 111 in the 1 mg group, and 148 in the placebo group (randomization ratio of 4:3:4).

5 Statistical Analysis Datasets

5.1 Pharmacokinetic Analysis Set

The pharmacokinetic analysis set will comprise subjects who have been treated with brexpiprazole and for whom plasma drug concentration data have been obtained, other than those deemed as "not analyzed" or "not determined."

5.2 Full Analysis Set

The full analysis set (FAS) will comprise subjects who, after randomization, have received at least 1 dose of the IMP, and from whom CMAI total scores have been obtained at baseline and at least 1 time point after initiation of the treatment.

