3.8.1.5 Examination at Discontinuation

At discontinuation, the investigator or subinvestigator will perform the observations, tests, and assessments shown in Table 3.8-1 as promptly as possible, within the same day if possible, after discontinuation has been decided and will record the results along with the date of visit. If at time of discontinuation, the subject or caregiver refuses any of the tests or if the investigator or subinvestigator judges that tests cannot be performed due to an emergency, only those observations, tests, and assessments that are feasible will be performed.

3.8.1.6 Follow-up Observation (Twenty-eight Days After Completion or Discontinuation of IMP Administration)

The investigator or subinvestigator will perform the observations, tests, and assessments shown in Table 3.8-1 and record the results and date of visit. These observations, tests, and assessments will also be performed in discontinued subjects unless the subject or caregiver refuses any of the tests or the investigator or subinvestigator judges that tests cannot be performed due to an emergency. Follow-up observation will not be performed for subjects who have transitioned to the extension trial and commenced IMP administration.

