5.3 Safety Analysis Set

The safety analysis set will comprise subjects who, after randomization, have received at least 1 dose of the IMP.

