7.6 Protocol Deviations

In randomized subjects, numbers and proportions of subjects with major deviations from the protocol will be determined for each deviation category (treatment-related deviations, eligibility-related deviations, failure to discontinue the trial when the subject meets the withdrawal criteria, procedure-related deviations that affect evaluation of the primary endpoint, use of prohibited medications, and overall) and each trial site, overall, for each treatment group, and for the overall brexpiprazole group.

8 Efficacy Analysis

Efficacy analyses will be performed on the FAS. Baseline is defined as the last data obtained prior to initiation of IMP treatment.

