8.1.2 Sensitivity Analyses

8.1.2.1 Sensitivity Analysis for Handling of Missing Data

As a sensitivity analysis for handling of missing data, placebo multiple imputation and tipping point analysis on MNAR assumption will be performed using a pattern-mixture model with multiple imputation.

Multiple imputation analysis will be performed according to the following procedure. The number of imputations will be 100.

- 1) The Fully Conditional Specification (FCS) method will be used to impute missing data. The imputation model for each period will include the medical care category (inpatient or outpatient) and prior use of antipsychotics (yes or no), as well as the CMAI total score for the preceding periods.
- 2) The same MMRM as that of the primary efficacy analysis will be used to analyze the multiple-imputed datasets.
- 3) The MIANALYZE procedure will be used to integrate the analysis results of the multiple-imputed datasets, and the estimate of the difference between each brexpiprazole group and the placebo group at Week 10 and its 95% CI and p-value will be determined.

In placebo multiple imputation, for discontinued subjects in each brexpiprazole group, MNAR will be assumed for missing data and an imputation model based on the placebo group will be used in imputation.

In tipping point analysis, for subjects in each brexpiprazole group who discontinued treatment for any of the following reasons, MNAR will be assumed for missing data after discontinuation.

- Withdrawal for any reason
- Withdrawal due to adverse events (AEs), a lack of efficacy, or consent withdrawal (by subject, legally acceptable representative, or caregiver)
- Withdrawal due to AEs or a lack of efficacy

For subjects in each brexpiprazole group who discontinued treatment for reasons assumed as MNAR, the MAR assumption will be used to impute missing data, add Δ (intergroup differences in MMRM of the primary efficacy analysis) \times k% to the imputed value after withdrawal, and increase k (with 200 as the upper limit) until a statistically significant conclusion is reversed (p > 0.05).

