CT-5.6.2	
CT-5.6.3	
CT-5.6.4	
CT-5.7.1	

CT-5.7.2	
CT-5.7.3	
CT-5.7.4	
CT-5.8.1	
CT-5.8.2	
C1-3.6.2	
CT 5.0.2	
CT-5.8.3	
CT-5.8.4	
CT-5.9.1	
CT-5.9.2	
C1-3.9.2	
CT-5.10.1	
CT-5.10.2	
C1-3.10.2	
CT-5.11.1	Sensitivity Analysis of MNAR using Tipping Point Analysis in CMAI Total Score
CT-5.11.2	Assume All Dropouts as MNAR (Full Analysis Set) Sensitivity Analysis of MNAR using Tipping Point Analysis in CMAI Total Score
C1 3.11.2	Dropout due to AE or LOE or Withdrew Consent as MNAR (Full Analysis Set)
CT-5.11.3	Sensitivity Analysis of MNAR using Tipping Point Analysis in CMAI Total Score
CT-5.11.4	Dropout due to AE or LOE as MNAR (Full Analysis Set) Sensitivity Analysis of MNAR using Placebo Based Imputation in CMAI Total
01 0.11	Score (Full Analysis Set)
CT-5.11.5	Summary of Mean Change From Baseline to Double Blind Treatment Period by
	Study Week in CMAI Total Score - Van Elteren Test, Robust Regression - MI (Full Analysis Set)
CT-5.11.6	Summary of Mean Change From Baseline to Double Blind Treatment Period by
	Study Week in CMAI Total Score - Van Elteren Test, Robust Regression - OC (Full
CT-6.1.1	Analysis Set) Summary of Mean Change From Baseline to Double Blind Treatment Period by
	Study Week in CMAI Total Score by Medical Care Category: In-patient - MMRM
CT (1 2	(Full Analysis Set)
CT-6.1.2	Summary of Mean Change From Baseline to Double Blind Treatment Period by Study Week in CMAI Total Score by Medical Care Category: Out-patient - MMRM
	(Full Analysis Set)
CT-6.2.1	Summary of Mean Change From Baseline to Double Blind Treatment Period by
	Study Week in CMAI Total Score by Prior Antipsychotics: Present - MMRM (Full Analysis Set)
CT-6.2.2	Summary of Mean Change From Baseline to Double Blind Treatment Period by
	Study Week in CMAI Total Score by Prior Antipsychotics: Absent - MMRM (Full
	Analysis Set)

CT-6.3.1	Summary of Mean Change From Baseline to Double Blind Treatment Period by Study Week in CMAI Total Score by Main Care Giver: Staff of Hospital - MMRM
CT-6.3.2	(Full Analysis Set) Summary of Mean Change From Baseline to Double Blind Treatment Period by Study Week in CMAI Total Score by Main Care Giver: Staff of Care Facility - MMRM (Full Analysis Set)
CT-6.3.3	Summary of Mean Change From Baseline to Double Blind Treatment Period by Study Week in CMAI Total Score by Main Care Giver: Family - MMRM (Full Analysis Set)

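### The placebo-imputation and tipping-point analyses run on the FAS, so treated subjects never re-rated on the CMAI are in no missing-data analysis

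*SAP*

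**What the plan says.** **Population.** The opening of SAP 8 states: "Efficacy analyses will be performed on the FAS". It makes no exception for the sensitivity analyses in 8.1.2. The FAS needs at least one dose and takes subjects "from whom CMAI total scores have been obtained at baseline and at least 1 time point after initiation of the treatment" (SAP 5.2; protocol 6.2.2 is the same). The set that keeps every dosed subject is defined in SAP 5.3: "The safety analysis set will comprise subjects who, after randomization, have received at least 1 dose of the IMP". No listed efficacy analysis uses it.

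**Missing-data analyses.** SAP 8.1.2.1: "As a sensitivity analysis for handling of missing data, placebo multiple imputation and tipping point analysis on MNAR assumption will be performed". In the placebo version, "for discontinued subjects in each brexpiprazole group, MNAR will be assumed for missing data and an imputation model based on the placebo group" is applied. The tipping point has three scenarios: withdrawal for any reason; withdrawal for AE, lack of efficacy or withdrawn consent; and withdrawal for AE or lack of efficacy. In SAP Appendix 5 the three tipping-point tables (CT-5.11.1 to CT-5.11.3) and the placebo-based table (CT-5.11.4, "Sensitivity Analysis of MNAR using Placebo Based Imputation in CMAI Total" Score) are all labelled as FAS tables. The title of CT-5.11.1 says that all dropouts are taken as MNAR.

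**When the CMAI is rated.** Protocol Table 3.8-1 schedules it at baseline, at Weeks 2, 4, 6, 8 and 10, and at discontinuation. There is none at Week 1. Protocol 3.8.1.5 wants the discontinuation examination done promptly, on the same day where possible. On refusal or in an emergency, however, "only those observations, tests, and assessments that are feasible will be performed".

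**The concern.** Whether a treated subject is in the FAS depends on what happens after randomisation. For the observed-cases MMRM this is ordinary, because a subject with no post-baseline score contributes nothing to that model in any case.

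The MNAR analyses have a different job. They ask whether the result would survive if those who left had done no better than placebo, or worse. Subjects who left before any further rating are the ones about whom least is known, and their absence is unlikely to be random. They can still be imputed: baseline CMAI, medical care category and prior antipsychotic use are on record, and the planned FCS model already uses the two factors and preceding CMAI scores. If they are left out, the all-dropouts scenario covers fewer subjects than its title suggests, and the placebo imputation gives the active arms no penalty for them.

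**Working it through.** **Who is in and who is out.** Take subjects who stop before Week 2.

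- *Discontinuation CMAI done on Days 2-11.* The subject is in the FAS. SAP Table 3.4-1 assigns the rating to Week 1, which is not an MMRM time point (SAP 8.1.1), so the subject adds no value to the primary model. Weeks 2-10 are missing and fall to be imputed. The SAP does not say whether the Week 1 value enters the imputation.
- *No CMAI after baseline.* The subject is outside the FAS and is not imputed.
- *CMAI only 7 or more days after the last dose.* SAP 3.4 drops such data from analysis. Whether that also removes the subject from the FAS is not stated.

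Two subjects who stop on the same day can therefore be treated differently because one refused the rating.

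**Planning figures (SAP 4, protocol 6.1).** Difference -5.35; SD 15.06; 148 / 111 / 148 subjects (2 mg / 1 mg / placebo); two-sided 5%.

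- SE, 2 mg vs placebo = 15.06 × √(2/148) = 1.751
- SE, 1 mg vs placebo = 15.06 × √(1/148 + 1/111) = 1.891
- Power by noncentral t: 86.1% and 80.5%. Both stated figures are reproduced (the normal approximation gives 86.3% and 80.8%).

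**Effect of restoring the omitted subjects.** Let q be the share of the active arm with no post-baseline CMAI. The documents give no value, so q is an assumption. The SE is held at its planning value.

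- *Placebo imputation:* restored subjects have no benefit over placebo, so the effect is -5.35 × (1 - q).
- *All-dropouts tipping point at k = 200%:* the MAR value (taken as -5.35 relative to placebo) is worsened by 2 × 5.35 and becomes +5.35. The effect is -5.35 × (1 - 2q).

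| q | 2 mg subjects | Placebo-imputed effect | Shift (share of SE 1.751) | Effect at k = 200% | Shift (share of SE) |
|---|---|---|---|---|---|
| 1% | 1.5 | -5.30 | 0.054 (3%) | -5.24 | 0.107 (6%) |
| 3% | 4.4 | -5.19 | 0.161 (9%) | -5.03 | 0.321 (18%) |
| 5% | 7.4 | -5.08 | 0.268 (15%) | -4.815 | 0.535 (31%) |

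These shifts are upper bounds. They start from -5.35, whereas the FAS sensitivity estimate is already pulled toward zero by the dropouts it does impute. If that estimate is -5.35 × (1 - r), restoring a share q with no benefit moves it by 5.35 × (1 - r) × q, which is at most 5.35q.

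**In terms of power.** The first row is the FAS with the same share absent from every arm and the effect unchanged. The second is all treated subjects with placebo-like values for the restored ones.

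| 2 mg / 1 mg | q = 1% | q = 3% | q = 5% |
|---|---|---|---|
| FAS only | 85.8% / 80.1% | 85.1% / 79.3% | 84.3% / 78.4% |
| All treated, placebo-like | 85.4% / 79.7% | 84.0% / 78.1% | 82.5% / 76.4% |

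**Distance from the threshold.** At q = 5%, z for 2 mg moves from 5.35/1.751 = 3.06 to 5.08/1.751 = 2.90. Losing significance at the planned effect needs 5.35 × (1 - q) = 1.96 × 1.751 = 3.43, so q is about 36%.

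**The case against.** *The group is small and narrowly defined.* A reader might infer that the earliest dropouts in general are missing, for example anyone who stops for an AE during titration. The documents do not support that. A CMAI is planned at discontinuation, and the FAS asks for any CMAI after the start of treatment, not one at a scheduled week. A typical AE stop during titration is therefore meant to be rated, enters the FAS and is imputed. This objection stands: the point concerns only subjects with no post-baseline CMAI.

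*The direction is not fixed.* A reader might also infer that the omission always favours the sponsor. That is not shown. It holds in expectation, given a true benefit, for the placebo imputation and the all-dropouts tipping point. In the other two tipping-point scenarios, an omitted subject who left for an unlisted reason would be imputed under MAR with no shift, so restoring that subject brings no systematic dilution.

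*A single population isolates the assumption.* If the MNAR analyses moved to a wider set while the MMRM stayed on the FAS, a difference between them would mix a change of population with a change of missing-data assumption. This is a sound argument against replacing the FAS versions. It is not an argument against adding a second version beside them.

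*The exclusions will be visible.* SAP 7.1 counts each analysis set by treatment group, and listing SUBEX-1 names the excluded subjects. That lets a reader bound the effect, but it does not test it.

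**Conclusion.** The gap is real and minor. As written, treated subjects with a baseline CMAI and no later rating are in neither the primary analysis nor any analysis of missing data.

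Under the planning values and a true benefit, the expected overstatement of robustness for 2 mg is at most 0.05 to 0.27 points in the placebo imputation, and at most 0.11 to 0.54 points in the all-dropouts tipping point at k = 200%, for an assumed 1-5% omitted. This would matter only for a result close to the significance threshold, or if the omissions were unbalanced between arms.

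The documents do not support reading this as an error in the FAS definition, a contradiction in the plan or a threat to the primary result. They report no omission rate and nothing that shows a changed conclusion.

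**What to change.** Leave the FAS in place for the primary MMRM, and keep the planned FAS sensitivity analyses. Add to SAP 8.1.2.1:

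*The placebo multiple imputation and the tipping-point analysis for withdrawal for any reason will be repeated in all randomised subjects who received at least one dose of IMP and have a baseline CMAI total score. Where no later score exists, Weeks 2 to 10 will be imputed from baseline CMAI, medical care category and prior use of antipsychotics. The subjects added relative to the FAS will be tabulated by treatment group and reason.*

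Two table shells would be added to Appendix 5. Protocol 6.3 leaves the details of these analyses to the SAP.

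The cost is a little extra programming and a different input dataset. The drawback is that values for a few subjects rest almost wholly on the imputation rule, which the tabulation makes plain. If few subjects are added, the results will barely move and the robustness claim is stronger for it.

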5.3 Safety Analysis Set

The safety analysis set will comprise subjects who, after randomization, have received at least 1 dose of the IMP.

5.4 Handling of Missing Data

The primary analysis of the primary endpoint will be performed in the observed cases (OC) dataset by mixed models for repeated measures (MMRM) without data imputation for missing data under the "missing at random" (MAR) assumption. As a sensitivity analysis for the handling of missing data, placebo multiple imputation and tipping point analysis will be performed under the "missing not at random" (MNAR) assumption. Details are described in Section 8.1.2.

For analyses of efficacy, safety, and other endpoints, the last observation carried forward (LOCF) method (in which missing post-dose data are imputed by the last observed data after initiation of IMP treatment) will be used as needed.

For pharmacokinetic analysis, no imputation will be performed for missing data.

6 Primary and Secondary Outcome Variables

6.1 Primary Endpoint

The primary endpoint is change in CMAI total score from baseline to Week 10.

6.2 Secondary Endpoints

- Changes in CMAI subscales (Aggressive Behavior, Physically Non-aggressive Behavior, and Verbally Agitated Behavior) from baseline to Week 10
- Change in Clinical Global Impression—Severity of Illness (CGI-S) from baseline to Week 10

• Clinical Global Impression—Global Improvement (CGI-I) at Week 10

7 Disposition and Demographic Analysis

7.1 Subject Disposition

Numbers and proportions of subjects from whom informed consent was obtained, those who were randomized, those who received trial treatment, those who completed the trial, those who discontinued the trial, those who discontinued the trial by reason for discontinuation, and those included in each analysis set will be summarized overall, for each treatment group, and for the overall brexpiprazole group.

7.2 Demographic and Baseline Characteristics

Descriptive statistics (mean, standard deviation, minimum, median, and maximum; hereinafter the same applies) of age, height, baseline body weight, and baseline body mass index (BMI), and frequency distribution of age category ($< 80, \ge 80$) ($< 65, \ge 65$ to $< 75, \ge 75$), sex, race, ethnicity, country where trial is conducted, complications, medical history, and CYP2D6 phenotype will be determined in each analysis set, overall, for each treatment group, and for the overall brexpiprazole group.

7.3 Baseline Disease Evaluation

Descriptive statistics of the duration of dementia of the Alzheimer's type, duration of agitation associated with dementia of the Alzheimer's type, baseline CGI-S, CMAI (total score, subscale scores), MMSE total score, and ADCS-ADL total score, and frequency distribution of medical care category, type of caregiver, prior use of antipsychotics, prior medication other than antipsychotics (for agitation associated with dementia of the Alzheimer's type), and concomitant use of antidementia drugs (yes or no) will be determined overall, for each treatment group, and for the overall brexpiprazole group.

The duration of dementia of the Alzheimer's type and the duration of agitation associated with dementia of the Alzheimer's type will be calculated using the following formula: duration (months) = (date of subject demographic evaluation – date of onset + 1) / 30. Any unknown month or day of onset will be replaced with June or 15, respectively.

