	group, a more sufficient power of detection will be obtained by
	changing the randomization ratio. In this trial, it is assumed that the
	difference between the 2 mg group and the placebo group in the
	change in the CMAI total score from baseline to Week 10 is -5.35 ,
	and the standard deviation (calculated from the standard error of the
	difference between the 2 mg and placebo groups and the number of
	subjects at baseline) is 15.06 on the basis of the results of Trial 331-
	12-283. By setting the number of subjects in the 2 mg group, 1 mg
	group, and placebo group as 148, 111, and 148, respectively
	(randomization ratio of 4:3:4), the power of detection is 86.1% for
	the comparison between the 2 mg group and the placebo group and is
	80.5% for the comparison between the 1 mg group and the placebo
	group in a test with a significance level of 5% (two sided).
	On the basis of the above considerations, the number of subjects will
	be set at 148 in the 2 mg group, 111 in the 1 mg group, and 148 in
	the placebo group (randomization ratio of 4:3:4).
Trial duration:	August 2018 to June 2023 (planned)
	The duration of participation in the trial by each subject will be up to
	20 weeks.

Table of Contents

Proto	col Synopsis	2
Table	of Contents	7
List o	f In-text Tables	13
List o	f In-text Figures	14
List o	f Appendices	15
List o	f Abbreviations and Definitions of Terms	16
1	Introduction	18
1.1	Background	18
1.2	Nonclinical Data	20
1.3	Clinical Data	21
1.3.1		
		21
1.3.1.1		21
1.3.1.2		23
1.3.1.3		25
1.4	Known and Potential Risks and Benefits	
2	Trial Rationale and Objectives	27
2.1	Trial Rationale	27
2.2	Rationale for CYP2D6 Genetic Testing and DNA Storage	
2.3	Rationale of Sample Storage for Biomarker Exploration	29
2.4	Trial Objectives	
3	Trial Design	
3.1	Type/Design of Trial	
3.2	Trial Treatments	32
3.2.1	Dosing and Regimen	32
3.2.2	Rationale for Dosing and Regimen	32
3.2.3	Rationale for Duration of Treatment	34
3.3	Trial Population	34
3.3.1	Number of Subjects and Trial Population	34
3.3.2	Subject Number Assignment	34
3.4	Eligibility Criteria	35

3.4.1	Informed Consent	35
3.4.2	Inclusion Criteria	36
3.4.3	Exclusion Criteria	38
3.5	Requirements for Caregivers	41
3.6	Endpoints	42
3.6.1	Primary Endpoint	42
3.6.2	Secondary Endpoints	42
3.6.3	Exploratory Endpoints	42
3.6.4	Safety Endpoints	42
3.6.5	Pharmacokinetic Endpoint	43
3.6.6	Pharmacogenomic Endpoint	43
3.6.7	Other Endpoints	43
3.7	Measures to Minimize/Avoid Bias	43
3.8	Trial Procedures	45

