3.4.2 Inclusion Criteria

Subjects must meet the inclusion criteria described in Table 3.4.2-1.

Tab	le 3.4.2-1 Inclusion Criteria
1	Patients who have provided written informed consent (or whose legally acceptable representative has provided written informed consent). If the investigator or subinvestigator judges that the patient is incapable of providing informed consent or is hospitalized for reasons related to medical protection, the patient's legally acceptable representative must provide written consent.
2	 Patients who meet both of the following diagnostic criteria: Diagnosis of "Dementia due to Alzheimer's Disease" according to the Diagnostic and Statistical Manual of Mental Disorders Fifth Edition (DSM-5).
	 Diagnosis of "Probable Alzheimer's Disease" according to the National Institute of Neurological and Communicative Disorders and Stroke–Alzheimer's Disease and Related Disorders Association (NINCDS-ADRDA).
3	Patients who are \geq 55 and \leq 90 years of age at the time of obtaining informed consent.
4	 Patients who can be followed in the same environment (as described below) from at least 3 weeks before baseline evaluation up to the completion of the examinations scheduled at the completion or discontinuation of investigational medicinal product (IMP) administration. Patients who will be hospitalized in the same medical facility.
	• Patients who will be institutionalized in the same care facility.
	• Patients who will continue to receive care at home. For patients receiving day care or day service, those patients who will visit the same care facility at the same frequency during the above-mentioned period will be included.
5	Patients whose caregiver can properly collect the necessary information (the main caregiver must observe the patient's condition in at least 4 days per week for 4 hours or more a day) Patients receiving home care must live with a specific caregiver and must not live alone.

Tab	ble 3.4.2-1 Inclusion Criteria
6	Patients with a Mini-Mental State Examination (MMSE) total score of ≥ 1 to ≤ 22 at screening.
7	
8	Patients who have agitation that interferes with daily activities and is persistent/recurs frequently during the 2 weeks each before the screening examination and baseline evaluation. Agitation is defined according to the "Consensus provisional definition of agitation in cognitive disorders" from
	the International Psychogeriatric Association (IPA). ^a

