3.8.1.1 Screening Period

To confirm that the subject meets the inclusion criteria and does not fall under the exclusion criteria, observations, tests, and assessments will be performed, and the results will be recorded after the date of informed consent but before the baseline assessment.

The caregivers will be provided with the subject diary for the period up to the baseline evaluation and be given an explanation on how to complete the subject diary, and instructed to record the required information in the subject diary from 14 days before the baseline evaluation until the baseline evaluation. In the subject diary, occurrence of daily symptoms will be recorded to evaluate the frequency of occurrence of agitation associated with dementia of the Alzheimer's type (CMAI).

The investigator or subinvestigator will record subject information related to the enrollment criteria, which had been collected during screening, in the eligibility form specified by the sponsor and submit to the medical monitor for confirmation of the subject's eligibility. The medical monitor will confirm the content of the eligibility form, and if there is any doubt regarding the subject's eligibility, he/she will consult with the investigator or subinvestigator to determine the subject's eligibility before the baseline examination.

The investigator or subinvestigator will investigate subject background and other information as follows and record it in the source document and CRF.

- Date of visit
- Date of informed consent by the subject (or their legally acceptable representatives) and caregivers
- Subject background information
 - Sex, date of birth, race, ethnicity, and trial country
 - Possibility of getting pregnant in women of childbearing potential (WOCBP) (see Section 5.5 Pregnancy) (if there is no childbearing potential, record the reason)
 - Diagnosis of dementia of the Alzheimer's type (diagnostic criteria of DSM-5 and NINCDS-ADRDA)
 - Timepoint of onset of dementia of the Alzheimer's type
 - Timepoint of diagnosis of dementia of the Alzheimer's type
 - Timepoint of onset of agitation associated with dementia of the Alzheimer's type
 - Complications
 - Medical history (for the 2 years preceding informed consent; however, medical history related to the inclusion/exclusion criteria is not limited to the preceding 2 years.)
 - Medical care category (inpatient or outpatient; if outpatient, institutionalized or care at home)

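### SAP 7.3 lets an imputed onset date fall after the evaluation date, so a baseline disease duration can come out negative

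*SAP*

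**What the plan says.** SAP 7.3 (Baseline Disease Evaluation) derives two durations, one for dementia of the Alzheimer's type and one for the associated agitation, with a single formula: "duration (months) = (date of subject demographic evaluation – date of onset + 1) / 30". For partial onset dates it adds: "Any unknown month or day of onset will be replaced with June or 15, respectively". There is no condition linking the imputed date to the evaluation date and no floor at zero. SAP Section 15, which lists changes to the planned analyses, adds none.

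Both durations get the standard descriptive statistics defined in SAP 7.2, which include the minimum, mean and SD. SAP Appendix 5 lists the baseline disease tables as CT-3.2.1 (full analysis set) and CT-3.2.2 (safety analysis set).

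On the protocol side, Section 3.8.1.1 has the site record the onset time point of agitation during screening, without stating how precise the date must be. Criterion 8 in Section 3.4.2 requires agitation that is "persistent/recurs frequently during the 2 weeks each before the screening examination and baseline evaluation". Nothing in the visible criteria asks for a longer history, so onset in the calendar year of evaluation is eligible.

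**The concern.** A fixed mid-year month is a reasonable substitute when the onset year is over by the time of evaluation. It fails when the onset year is the evaluation year and the evaluation comes before mid-June: the imputed onset then lies in the future. The subject's onset had already been recorded at the evaluation, and for agitation criterion 8 puts it before screening, so a zero or negative duration cannot be right.

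The SAP plainly expects unknown months, since it has a rule for them. The planned trial period, August 2018 to June 2023, contains every January-to-June interval from 2019 to 2022 and the early part of 2023. What is at stake is the credibility of a baseline table. One affected subject is enough to print a negative minimum, and a programmer who corrected it silently would be departing from the SAP without a record.

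**Working it through.** The plan states no duration figure, so there is none to reproduce. The check applies the SAP formula to the case the rule leaves open.

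**Inputs**
- Formula (SAP 7.3): duration = (E - O + 1) / 30, where E is the evaluation date and O the onset date, with the difference in days.
- Imputation (SAP 7.3): an onset known only by year becomes 15 June of that year.
- Shortest agitation history (Protocol 3.4.2, criterion 8): about 14 days. I assume that this can be counted back from the demographic evaluation.

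**Step 1. Onset recorded as 2019 only, so O = 15 June 2019**

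| Evaluation (2019) | E - O (days) | (E - O + 1) / 30 | Months |
|---|---|---|---|
| 15 January | -151 | -150 / 30 | -5.00 |
| 1 February | -134 | -133 / 30 | -4.43 |
| 1 March | -106 | -105 / 30 | -3.50 |
| 1 April | -75 | -74 / 30 | -2.47 |
| 1 May | -45 | -44 / 30 | -1.47 |
| 13 June | -2 | -1 / 30 | -0.03 |
| 14 June | -1 | 0 / 30 | 0.00 |
| 15 June | 0 | 1 / 30 | 0.03 |

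Evaluations on 1 to 14 January are left out: 14 days of agitation would then put the onset in the previous year. In a leap year 15 January gives -151 / 30 = -5.03.

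**Step 2. What the true value could be.** For the 1 February 2019 evaluation, an onset in 2019 at least 14 days earlier lies between 1 and 18 January. The possible durations run from (14 + 1) / 30 = 0.50 to (31 + 1) / 30 = 1.07 months. The rule returns -4.43, an error of -4.43 - 0.50 = -4.93 to -4.43 - 1.07 = -5.50 months.

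**Step 3. Effect on the table.** One such subject makes the arm's minimum -4.43. The shift in the arm mean is the error divided by the arm size. With the planned numbers, and assuming that all are analysed:
- 148 subjects: -4.93 / 148 = -0.033 to -5.50 / 148 = -0.037 months.
- 111 subjects: -4.93 / 111 = -0.044 to -5.50 / 111 = -0.050 months.

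The minimum is visibly wrong from one case. The mean moves little unless there are many.

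**Step 4. Unknown day only.** With the month known, the day-15 rule can also overshoot: onset in March with day unknown, evaluated on 1 March, gives (-14 + 1) / 30 = -0.43 months. For agitation the 2-week criterion makes this unlikely; for dementia duration no such criterion applies.

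**The case against.** The strongest reply is that this hardly matters. A negative value from a year-only date needs three things together: the onset month unknown, onset in the evaluation year, and evaluation before 14 June. No section says how often the month is unknown or how recent onset tends to be, and for dementia a same-year onset is less likely than for agitation. The number affected may be zero. All of that stands, and it sets the weight of the point. It does not rescue the rule, which returns an impossible value whenever the case arises.

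Three stronger readings are tempting and are not supported:

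- **A large share of subjects is affected.** One can count dates. Of the 351 evaluation dates in 2019 from 15 January on, 150 give a negative value (150 / 351 = 42.7%). If each date is instead weighted by the number of possible onset days, 1 up to 351, the share is (150 × 151 / 2) / (351 × 352 / 2) = 11,325 / 61,776 = 18.3%. Both figures apply only to subjects with a same-year onset and an unknown month. The documents give neither their number nor their dates, so no share of subjects or average error can be stated for the trial.
- **Dividing by 30 is an error.** SAP 7.3 states the divisor openly and applies it to every subject and arm. It is a disclosed unit convention.
- **Efficacy results are at risk.** The durations are not in the primary model (SAP 8.1.1), the allocation factors (Protocol 3.8.1.3) or the visible efficacy subgroups (SAP 8.3).

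**Conclusion.** The point holds as a minor fault in a derivation rule. Followed to the letter, SAP 7.3 gives a negative duration to any subject whose onset is known only as the evaluation year and who is evaluated before 14 June. For agitation the values run from about -5.0 to -0.03 months for evaluations from 15 January to 13 June, with zero on 14 June. The lower end assumes a 14-day history counted back from the evaluation; the sign of the result does not depend on that assumption.

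The consequence is confined to the descriptive duration statistics in CT-3.2.1 and CT-3.2.2: the minimum first, then slightly the mean and SD. The number of subjects affected is unknown, and nothing inferential changes.

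**What to change.** Add one sentence to SAP 7.3: if the imputed onset date would fall after the "date of subject demographic evaluation", replace it with a date within the known partial period that is not later than the evaluation. A suitable choice is the midpoint between the earliest possible onset date and the evaluation date. For agitation, the date should also be no later than 14 days before the evaluation where the known partial date allows. Leave the June/15 rule unchanged for all other dates and keep the divisor of 30.

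Checks on the wording:
- Evaluation 1 February 2019, onset 2019: the midpoint is 16 January, giving (16 + 1) / 30 = 0.57 months, inside the possible range of 0.50 to 1.07.
- Evaluation 20 January 2019, onset 2019: the midpoint is only 9.5 days back, so for agitation the 14-day clause moves the onset to 6 January, giving (14 + 1) / 30 = 0.50 months.
- Simply capping the onset at the evaluation date gives 1 / 30 = 0.03 months. That removes the negative value but sits less well with criterion 8.

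The cost is one SAP sentence and about one line of derivation code. No inferential analysis changes. If the SAP is already in use, the same sentence can be recorded as a clarification in the study report.
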